In tissue culture studies, in human studies and in animal studies when inhaled or applied topically, sodium pyruvate inhibited the ability of many viral strains from replicating due to the ability of Sodium Pyruvate to increase the synthesis of Nitric Oxide that is needed to kill infections.

Mice studies conducted by [name] at Missouri State University substantiated our finding by testing nebulized N115 in flu (influenza A H1N1 virus) infected mice that decreased morbidity, weight loss, proinflammatory cytokines, and decreased viral titers (virus numbers) compared to the Placebo Control. Additionally, treated mice consumed more chow during infection indicating improved symptoms (same results reported in a pilot mice COVID-19 study). There were notable improvements in pro-inflammatory cytokine production (IL-1 β) and lower virus titers (viral numbers) on days 7 post infection in mice treated with Sodium pyruvate compared to the Placebo Control animals. As pyruvate acts on the host immune response, metabolic pathways and not directly on the virus, our data demonstrate that sodium pyruvate is a promising treatment option that is safe, effective, and unlikely to elicit antiviral resistance.

Furthermore, they stated "we have preliminary data that suggest it may work similarly during other respiratory virus infections including COVID19/SARS-CoV-2. Proactive treatments with sodium pyruvate is not toxic and could be of benefit to children that are afflicted by many respiratory viruses".

Sodium Pyruvate Ameliorates Influenza A Virus Infection In Vivo - Online Research Posting on BioRxiv:

https://www.biorxiv.org/content/10.1101/2020.11.25.396978v1

A clinical survey of 367 patients over a two-year period demonstrated a statically significant decrease in the number, symptoms, and severity of seasonal Flu respiratory tract infections after using the 20mM sodium pyruvate nasal spray (EmphyCorp, N115). The number of flu or colds was reduced by 70% in Children and approximately 52% in Pregnant Women, Patients with Allergic Rhinitis, Diabetes, and Pulmonary Fibrosis.

In numerous human clinical trials (17, phase I, II, III clinical trials) submitted to the FDA, with Pulmonary Fibrosis, COPD and Cystic Fibrosis patients, N115 reduced nasal and lung inflammation and congestion by reducing inflammatory cytokines including the IL-6 cytokine that causes the so-called cytokine storm with no known adverse reactions.

In a Phase III Placebo Controlled Clinical Trial with Idiopathic Pulmonary Fibrosis Patients, N115 Non-Steroidal Nasal Spray demonstrated a statistically and clinically significant increase in Nasal Nitric Oxide, FEV-1, SaO2, FVC, FEV-1/FVC ratios (52% to 86%), and a significant reduction in coughing, nasal and lung inflammation. *N115 alleviated the symptoms associated with the COVID-19 infections in Patients with COPD and Pulmonary Fibrosis.* EmphyCorp has treated over 3 million Patients globally in 200 hospitals with no adverse events and has 17 human clinical trials that have been submitted to the FDA to support our NDA Phase III marketing application. Over a million patients in that group were patients with allergic rhinitis and as stated by the FDA 24% of their symptoms were caused by nasal infections predominantly colds and flu.

1.1.2 Background and Product Description

N115 is a sodium-pyruvate-based inhalation drug. It has been administered via several routes including intravenous, topical administration for hyperkeratotic disorders, and as an enteral supplementation since it is considered GRAS (Generally Regarded as Safe) by the FDA. Sodium pyruvate is used in many products including (Neosporin, Lubriderm, vaginal products, Viva Eye Drops, Ringers Solution, human IV solutions, and solutions to store red blood cells by the Red Cross, and to store human organs for transplant). Sodium pyruvate has been shown to protect neurons, lungs, hearts, muscles, cerebral metabolism, embryos, eyes, kidneys, cellular DNA and membranes from oxygen radical damage. Other approved uses in patients with a variety of medical disorders include Friedreich's disorder; and it is used as a therapeutic solution in open heart surgery, kidney surgery, and eye surgery.

Six different nasal spray formula combinations were tested for safety and efficacy in a series of studies with subjects who normally use nasal sprays. The sodium pyruvate concentrations were 5mM, 10mM, 20mM and 40mM. The sodium pyruvate was delivered in sterile sodium chloride solutions of either 0.45% or 0.90%. All formulas reduced inflammation in the nasal cavities and otherwise improved the nasal cellular morphology. There weren't any adverse events observed.

Additionally, safety and efficacy were tested for four weeks in patients with pulmonary fibrosis (PF), where it was determined that there was proven efficacy in reducing the conditions of PF, while no adverse events were reported. In a Phase III Placebo Controlled Clinical Trial with Idiopathic Pulmonary Fibrosis Patients, N115 demonstrated a statistically and clinically significant increase in FEV-1, SaO2, FVC, FEV-1/FVC ratios (52% to 86%), and a significant reduction in coughing, nasal inflammation, and congestion. Nasal inflammation and congestion block the release of nasal nitric oxide. Blockage of nitric oxide increases the rate and severity of infections. In our human Phase II/III Placebo Controlled Clinical Trials, N115 reduced nasal congestion and inflammation. In additional six human clinical trials with COPD patients submitted to the FDA, N115 demonstrated a significant decrease in nasal and lung inflammation, substantial increases in lung functions, and increased nitric oxide needed to kill invading bacteria These are critical benefits for treating the symptoms of Covid-19, as lung and viruses. inflammation leads to pneumonia and death. Improving lung function of Covid-19 patients can save lives. Increased nasal nitric oxide is a preventative to reduce the rate, duration and spread of the disease.

1.2 History of N115 Drug Use

N115 is all-natural, non-steroidal, and has no known side effects. It has been used successfully by over 2 million patients globally in over 200 hospitals during the past 5 years to treat nasal and lung inflammation, congestion in Patients with COPD, Allergic Rhinitis, Pulmonary Fibrosis, and Cystic Fibrosis. It has been used in Children, Diabetics, and Hypertensives, with efficacy and with no known side effects. It has even been shown to be safe

for use by Pregnant Women, for whom steroids are contraindicated as they increase the risk of low birth-weight babies.

1.3 Mechanism of Action

The upper and lower airways form one contiguous and functionally related organ that is critical to normal lung functions. The nasal cavity produces 900-1,100 parts per billion of nitric oxide, which is used to kill invading bacteria, fungi, and viruses, compared to the lungs which produce 4-48 parts per billion nitric oxide. Nasal nitric oxide is a natural defense against disease. In recent clinical studies, Nitric oxide is elicited and inhibits viral replication in pigs infected with porcine respiratory coronavirus. Nasal nitric oxide also produces clinically useful bronchodilation and has been shown to reduce pulmonary fibrosis. Blockage of nasal nitric oxide by inflammation or congestion, reduces the amount of nitric oxide reaching the lungs, which reduces critical lung functions, leading to increased lung and nasal infections, a reduced SaO2 level, reduced FEV-1 levels also leading to mouth breathing and coughing. Nasal nitric oxide is also essential because it 1) increases oxygenation in your blood by inhaling more nitric oxide, which is a vasodilator and bronchodilator that increases oxygen transport throughout the body. 2) Warms, moistens and filters the air. 3) Traps particles in nose hairs and mucous membranes. 4) Helps reduce the likelihood of developing colds, flu, allergies, and irritating cough. 5) Prevents nasal dryness. 6) Helps relieve stress and calm the body as it slows breathing. 7) Promotes healthy digestion. 8) reduces risks of developing snoring or sleep apnea. Nasal steroids and other OTC nasal treatments shut down the synthesis of nasal nitric oxide, which then leads to decreased lung functions and a 34% increase in infections.

As cited in hundreds of peer reviewed publications, naturally occurring nitric oxide in the nasal cavities is a primary defense in humans; it is needed to kill invading bacteria, fungi and viruses. Nasal nitric oxide also prevents and reduces the rate and severity of viral infections, viral replication from Rhinoviruses, the Flu, and Coronavirus.

Nitric oxide decreases significantly from the normal levels found in young healthy adults when compared to patients with Asthma, COPD, Diabetes, Cystic Fibrosis, and Primary Ciliary Dyskinesia. The rate of infection increases with decreasing levels of nasal nitric oxide.

1.4 Nasal nitric oxide and COVID-19 infections.

Nasal Nitric Oxide reduces the rate, duration and severity of viral infections in healthy young children and in healthy adults from the Flu, Rhinovirus and Coronavirus. It's been demonstrated that Nitric oxide is elicited and inhibits viral replication in pigs infected with porcine respiratory coronavirus. Nasal Nitric Oxide levels decreases from normal levels found in healthy adults, in patients with asthma (87%), COPD (73%) CF (44%) and Primary Ciliary Dyskinesia (7%). The rate of infections increases with decreasing levels of nasal nitric oxide. Young children, 6-17 years of age, produce (142%) more nitric oxide than healthy adults, which may explain their resistance to COVID-19. Recently, researchers announced that a high percentage of COVID-19 infected patients that were hospitalized were Diabetics or were Pre-Diabetic. The literature has reported that elevated levels of glucose in patients with diabetes mellitus cause a deficiency in the production of nitric oxide by blunting nitric oxide synthesis.

which may explain their susceptibility to COVID-19. N115 increases nitric oxide and is safe for use by Patients with Diabetes.

As cited in hundreds of peer reviewed publications, naturally occurring nitric oxide in the nasal cavities is a primary defense in humans. Nitric Oxide is needed to kill invading bacteria, fungi and viruses, and prevents/reduces the rate, duration and severity of viral infections, viral replication from the Common Cold, Rhinoviruses, the Flu, and Coronavirus. N115 Increases Nasal Nitric Oxide thus is a preventative to reduce the rate and spread of the disease.

Most Diabetic, Hypertensives, Pulmonary Fibrosis and Cystic Fibrosis Patients have very low nasal nitric oxide which makes them more susceptible to viruses and lung infections. The rate of infection increases with decreasing levels of Nasal Nitric Oxide making them more susceptible to all infections including COVID-19. Elevated levels of glucose in patients with diabetes mellitus cause a deficiency in the production of nitric oxide by blunting nitric oxide synthesis, which may explain why diabetics have a high susceptibility to COVID-19.

2.0 COVID-19 and flu Infection.

COVID-19 and flu can be understood by the region of the lung that is infected. Mild disease will be confined to the conducting airways and severe disease will involve the gas exchange portion of the lung. Both flu and COVID-19 are a major health concern and can be devastating, especially for the elderly. COVID-19 is the disease caused by SARS-CoV2 the virus. Although much is known about the mortality of the clinical disease, much less is known about its pathobiology. Although details of the cellular responses to this virus are just emerging, a probable course of events can be postulated based on past studies with SARS-CoV. Based on the cells that are infected, COVID-19 can be divided into three phases that correspond to different clinical stages of the disease. Stage #1: Asymptomatic state (Initial 1–2 days of infection); Stage #2: Upper airway and conducting airway response (Next few days), and, Stage #3 Hypoxia, ground glass infiltrates, and progression to ARDS. Flu can also result in a descending, progressive disease resulting in pneumonia and ARDS in severe cases.

Purpose and Objectives of the Studies.

A COVID-19 Non-Steroidal Nasal Spray Treatment and Preventative that can get athletes, students and the general population, that test positive for Covid-19, back playing and back to work much faster than a 14-day quarantine and as a Preventative to help reduce the rate, duration and spread of the virus, is critical to the world. In testing patients with the saliva/sputum test developed by Yale University, it was discovered that some actively infected patients may be asymptomatic, but remain infected, in some cases for three weeks or longer. Thousands of data points have been collected with the saliva/sputum tests on the duration of the infection in COVID-19 patients. This data will be used as a historical baseline to demonstrate a reduction and duration of the infection in patients that use the N115 nasal spray.

This will be an on-going trial that will study the effects of a 20mM sodium pyruvate in 0.9% sodium chloride nasal spray solution on COVID-19 viral infections of patients with proven COVID-19 infections.

1. Nasal-pharyngeal swabs that are currently FDA approved for testing COVID-19 patients, will be used to determine if an individual is actively infected.

- Covid-19 positive individuals will receive the nasal spray that will be used three times per day. This spray will be placebo control (15 patients, 0.9% sodium chloride with 0.02% benzalkonium chloride) or N115 treatment (15 patients, 20mM sodium pyruvate in 0.9% sodium chloride with 0.02% benzalkonium chloride). Study staff and subjects will be blinded.
- 3. Patients will return for testing again every other day to determine how fast the nasal spray reduces the viral load and infection, compared to the viral loads and infection on Day Zero, historical baselines, and placebo.

EmphyCorp Rx N115 Non-Steroidal Nasal Spray increases nasal nitric oxide and has the potential of reducing the rate and spread of COVID-19 among healthy individuals, diabetics, and others. Nasal steroids and other OTC nasal treatments shut down the synthesis of nasal nitric oxide which increases the rate of infections. This would indicate that the use of EmphyCorp's Rx N115 Nasal Spray by healthy individuals including Adults, Children, Pregnant Women, and Diabetics that are currently infected with COVID-19 without other underlying health conditions, could reduce the rate, duration and spread of infection.

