5.2. Institutional Review Board

5.3 Study Objectives

Primary Objective

- a. The primary objective is to evaluate the effects of inhaled nasal sodium pyruvate (N115) in patients with confirmed COVID-19 or flu infections by determining changes in the duration of an active infection by PCR from nasal.
 Secondary Objective
- **a.** The second objective is to evaluate the ability of the inhaled nasal sodium pyruvate therapy in subjects with COVID-19 or flu infections to improve symptoms by the use of a patient diary and by collecting periodic vital signs, especially body temperature, blood pressure and pulse/Ox.

5.4. Study Design Overview

Individuals that are symptomatic for COVID19/influenza will initially be tested by Dynamic DNA Labs or Trinity Healthcare (Screening Visit). If positive for COVID19/influenza, patient will then be solicited for participation in the trial within 24 hours. After signing Informed Consent, women of child-bearing age will provide a urine sample to test for pregnancy. They will be randomly assigned to either the placebo or drug groups in a double blinded fashion and be given a data logbook, or clinical app for their phone, in which they will record the number of coughs and other flu-like symptoms they experience each day. Patients will be contacted by phone and/or sent reminders through a clinical phone app every two days to review symptoms and protocol compliance and patients will be tested via nasal swab every other day. This will continue every other day until the subject tests negative for COVID-19/ influenza (which is

defined as a 2-Log reduction in virus titer or less than 1000 copies of viral RNA) or 14 days, whichever comes first. Personnel collecting swabs will wear N95 mask and face shield, disposable examination gloves and disposable gown while collecting nasal swabs from patients. Samples will be collected outdoors, weather permitting, or in a well ventilated room in inclement weather.

6.0. The criteria for patient selection and for exclusion of patients, and an estimate of the number of patients to be studied.

6.1. Subject Selection

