6.1.1 Number of Patients to be Studied

Fifteen patients with confirmed COVID-19 infection will be enrolled in the trial in the drug group and fifteen with confirmed COVID-19 infection will be enrolled in the trial in the placebo group. An additional fifteen patients with confirmed influenza infection will be enrolled in the trial in the drug group and fifteen with confirmed influenza infection will be enrolled in the trial in the placebo group. Efforts will be made to include women and minorities. The study will be double blinded to subjects and study investigators.

6.2. Inclusion Criteria

- **6.2.1.** Individuals with a confirmed COVID-19/influenza viral infection, as determined by a qualified laboratory test. A nasal swab or saliva test analyzed by qPCR for COVID19 or rapid flu test from nasal swab for influenza.
- **6.2.2.** Individuals who agree to abstain from sexual intercourse, or agree to use condoms or vaginal diaphragms or other devices designed to prevent contraception, during the entire course of the study

6.3. Exclusion Criteria

- **6.3.1.** Viral infections other than COVID-19 or influenza.
- **6.3.2.** Clinically significant cardiac disease including uncontrolled congestive heart failure and unstable angina
- 6.3.3. Pregnancy
- **6.3.4.** Females of child bearing potential age not on adequate contraception or lactating
- **6.3.5.** Subjects receiving systemic corticosteroid treatment within one month of Screening Visit
- 6.3.6. Subjects Less than 18 years of age
- **6.3.7.** Hospitalization within last 6 months due to acute exacerbation of airway disease
- **6.3.8.** Subjects with a clinically significant abnormal chest x-ray within past 12 months
- **6.3.9.** Medication changes within one month of study entry
- **6.3.10.** Subjects who have participated in another investigation drug treatment study within the previous month.
- **6.3.11.** Subjects with a current history of alcohol or recreational drug abuse.
- **6.3.12.** Subjects who have taken dietary supplements containing pyruvate within 24 hours prior to the screening visit.

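### Historical saliva/sputum durations are given the job of showing that N115 works, and nothing makes randomised placebo the deciding comparison

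*Combined protocol and SAP*

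**What the plan says.** The unnumbered section on purpose and objectives, which follows section 2.0, describes the historical data: "Thousands of data points have been collected with the saliva/sputum tests on the duration of the infection in COVID-19 patients". It adds that "some actively infected patients may be asymptomatic, but remain infected, in some cases for three weeks or longer". It then gives these data a purpose: "This data will be used as a historical baseline to demonstrate a reduction and duration of the infection in patients that use the N115" spray. Item 3 of the same section says that swab results will be "compared to the viral loads and infection on Day Zero, historical baselines, and placebo", with no ranking of the three.

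Section 5.3 sets the primary objective as an evaluation of N115 "by determining changes in the duration of an active infection by PCR from nasal". As printed, it names no comparator.

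Sections 7.1 and 7.2 describe a double-blind, placebo-controlled trial with randomisation to N115 or placebo. Section 18.2 ties ANOVA, chi-square and Fisher tests to N115 versus placebo. It then says the data will also be compared with public data described as matched, without naming a source or any matching variable.

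Section 6.1.1 plans 15 N115 and 15 placebo patients with COVID-19, and the same again for influenza ("An additional fifteen patients with confirmed influenza infection will be enrolled in the trial in the drug group", plus 15 on placebo). No section states a primary comparison, a hypothesis or a success criterion.

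**The concern.** A randomised placebo group shares the trial's specimen, negativity rule, visit schedule and stopping day with the treated group, so these features cancel. A historical group shares none of them by design. If it differs on any, a shorter duration on N115 may reflect how infection was measured and not the spray.

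The only comparison that the protocol says will demonstrate a reduction is the historical one. Followed as written, the Purpose section lets the sponsor conclude that N115 shortened COVID-19 infection even if N115 and placebo look alike. Small arms raise the risk: the valid comparison may be inconclusive while the other looks positive, and nothing in the text says which one governs.

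**Working it through.** **1. Are the two sources alike?**

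| Feature | Historical data (Purpose section) | Trial (sections 5.4, 6.1.1, 7.3.3) |
|---|---|---|
| Specimen | Saliva/sputum | Nasal swab |
| Virus | COVID-19 only | COVID-19 and influenza |
| Case mix | Includes some asymptomatic patients | "Individuals that are symptomatic for COVID19/influenza will initially be tested" (but criterion 6.2.1 does not require symptoms) |
| Negative result | Not stated | "defined as a 2-Log reduction in virus titer or less than 1000 copies of viral RNA) or 14 days, whichever comes first" |
| Longest duration | Three weeks or more in some cases | Follow-up ends at 14 days |
| Time origin | Not stated | Day 0, Visit 1 |

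The follow-up difference favours N115: a three-week infection counts at least 21 − 14 = 7 days longer in the historical data than the trial can record. There is no historical baseline at all for the 15 + 15 = 30 influenza patients.

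**2. Effect of a given gap.** The plan states no alpha, SD or effect size, so there is no plan figure to reproduce. Assume two-sided 0.05, no drug effect and 15 N115 patients. Let the historical mean be longer by d SD for non-drug reasons.

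- Historical mean treated as known: one-sample t test, 14 df, noncentrality d√15.
- History of m patients: two-sample t test, 13 + m df, noncentrality d√(15m/(15 + m)).

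| d | Noncentrality, mean known | False 'shorter', mean known | m = 50 | m = 200 | m = 1000 |
|---|---|---|---|---|---|
| 0.25 | 0.97 | 14.5% | 13.1% | 15.1% | 15.9% |
| 0.5 | 1.94 | 43.8% | 38.7% | 46.0% | 48.4% |
| 1.0 | 3.87 | 94.9% | 91.7% | 96.1% | 97.0% |

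Against concurrent placebo the rate is 2.5%, because d is zero.

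**3. Power of the valid comparison.** Two-sample t test, 15 versus 15, 28 df, noncentrality d√7.5: power is 26% at 0.5 SD and 75% at 1.0 SD. Power of 80% needs 1.06 SD.

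**4. What the 14-day stop alone can do.** Simulation, 20,000 null trials per setting. Durations are lognormal with assumed medians of 8 to 14 days and log-SD 0.4 or 0.6. Trial durations are cut at 14 days and compared with the uncut historical mean.

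- Median 8, log-SD 0.4: false 'shorter' 6.4%.
- Median 10, log-SD 0.4: 13.3%.
- Median 12, log-SD 0.4: 57.6%.
- Median 14, either log-SD: essentially 100%.
- Against placebo: 2.2% to 2.6% throughout.

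**5. What the 2-log rule alone can do.** Let L be the baseline log10 copies and r the fall in log10 per day. Trial time is min(2, L − 3)/r. Historical time is (L − 3)/r for a limit of 1000 copies, or (L − 2)/r for 100. With assumed L from 4.5 to 7 and r from 0.3 to 0.7:

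- Largest gap, L = 7, r = 0.3, limit 100: 5/0.3 − 2/0.3 = 16.7 − 6.7 = 10.0 days. With the trial time rounded up to the next two-day visit: 16.7 − 8 = 8.7 days.
- Smallest gap: 0 in continuous time for L up to 5 with a limit of 1000. With visit rounding in the trial only, L = 4.5, r = 0.7, limit 1000: 2.1 − 4 = −1.9 days, which goes against N115.

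Patient variation was then added by simulation (20,000 null trials per setting): L normal with SD 0.75 and a floor of 3.5, r lognormal with CV 50% and mean 0.3, 0.45 or 0.7. The historical limit was 1000 copies, historical times were either rounded to visits or not, and there was no 14-day cap.

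| Mean baseline | False 'shorter' versus history | Versus placebo |
|---|---|---|
| 10^4.5 | 0–13% | 2–3% |
| 10^5 | 0–29% | 2–3% |
| 10^6 | 42–90% | 2–3% |
| 10^7 | 97–100% | 2–3% |

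Adding the 14-day cap leaves the historical rates similar or raises them. Placebo stays at 2–3%.

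**The case against.** The strongest reply is that the operative sections already settle the matter. Section 7.0 is the place for naming the control group, and 7.1 and 7.2 answer with randomised placebo. Section 18.2 attaches its named tests only to N115 versus placebo, and its line on public data can be read as descriptive. The saliva/sputum baseline appears only in the Purpose narrative. On this view there is an inconsistent sentence, not a planned historical test.

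Much of that is fair. Placebo is implied to lead, and no test against history is specified, so the error rates above describe an analysis that the text permits, not one that it lays out. But implication does not fix the basis for a claim. The Purpose section is current text, and section 18.2 carries an external comparison into the analysis.

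Other points stand in part:

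- The simulated results run from no bias to near certainty, so they do not locate the actual bias.
- The case-mix contrast is soft. Section 5.4 starts from symptomatic people, but criterion 6.2.1 does not require symptoms, and matching might narrow the difference. With no matching variables named, that cannot be judged.
- The primary objective's sentence looks unfinished, so its missing comparator carries little weight alone.
- No paired test against Day Zero is planned. Item 3 only needs to avoid being read as an efficacy comparison, since a fall from Day Zero includes natural clearance.

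None of this removes the differences in specimen, stopping day and virus, or the unstated historical negativity rule.

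**Conclusion.** The concern holds. The plan assigns historical durations a demonstrating role, lists comparators without ranking them, and never makes randomised N115 versus placebo the deciding comparison. That gap in the wording is certain.

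The size of the consequence is conditional. It rests on an assumed two-sided 0.05 and, for the mechanisms, on assumed baselines, clearance rates, duration distributions and historical limits, none of which the documents give. Under those assumptions a non-drug gap of half an SD already produces a false finding in about 44% of trials. The bias may be nil at low baseline viral loads and close to certain at high ones. Against concurrent placebo the false 'shorter' rate stays at 2–3% in every setting tried. The trial does contain a valid comparison; what is missing is a statement that protects its primacy.

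**What to change.** - **Purpose section (including item 3) and section 18.2:** state that efficacy is judged solely on N115 versus concurrent randomised placebo, separately for COVID-19 and influenza. Enrolment is set per virus and the historical data cover only one of them.
- **Section 5.3:** complete the primary objective by naming concurrent placebo as the comparator.
- **Purpose section:** replace the wording that has historical data demonstrate a reduction with wording that gives them as descriptive context.
- **Historical, public-data and within-arm Day Zero comparisons:** report them descriptively, without p-values or efficacy claims. For any external data shown, give the specimen, negativity rule and time origin.
- **Keep Day Zero** as the reference for the 2-log rule (sections 5.4 and 7.3.3) and as the baseline covariate (section 18.2).

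Calling external data supportive would cure the ranking alone. Dropping p-values goes a step further, because a significance test across unlike measurements cannot be interpreted as a drug effect.

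The cost is protocol and SAP wording. Patients, treatment and sample size do not change. The sponsor gives up a comparison that might look favourable but could not support an efficacy claim, and must accept that 15 versus 15 per virus may be inconclusive.
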